10.2.2 Co-Primary endpoint

Based on feedback from the FDA, the co-primary endpoint is Technical Success OPTIMAL (measured at exit from the catheterization laboratory). This differs from "Technical Success ACCEPTABLE" only in the magnitude of the peak LVOT gradient.

All of the following must be present:

- Successful LAMPOON traversal and laceration; and
- Peak LVOT gradient < 30 mm Hg; and
- Absence of procedural mortality; and
- Successful access, delivery, and retrieval of the LAMPOON device system; and

- Successful deployment and correct positioning of the first intended device; and
- Freedom from emergency surgery or reintervention related to the device or access procedure.

10.2.3 Exploratory Endpoints

- LVOT obstruction measured as a pressure gradient on catheterization and echocardiography
- Incidence of LVOT obstruction > 20 mm Hg before discharge and at 30 days, including as an alternative LVOT gradient threshold to the primary endpoint
- Predicted neo-LVOT area based on THV frame had LAMPOON not been performed
- MVARC 30-day Device Success
- MVARC 30-day Procedure Success
- MVARC 1-year Patient Success
- Mortality, all-cause, cardiovascular vs non-cardiovascular, peri- vs non-periprocedural, LAMPOON and TMVR relatedness)
- Neurological events as reported by the site clinicians only
- Pre-discharge stroke, alone, and in combination with the primary endpoint
- Myocardial infarction
- Access and vascular complications
- MVARC bleeding complications
- AKIN acute kidney injury
- Arrhythmia and conduction disturbances
- Freedom from infection related to the TMVR at each time point
- Freedom from hemolytic anemia related to TMVR/LAMPOON
- Device related technical failure: Device Failure, Paravalvular Leak, Pericardial effusion, Conversion to open surgery, Device mal-positioning or migration or detachment, Device fracture, Unintended damage to native mitral valve apparatus
- Aortic valve regurgitation change
- Device thrombosis
- Outcomes of subjects greater than 65 years (i.e. eligible for Medicare based on age), to determine generalizability to the Medicare population¹

10.2.4 Rationale for primary endpoint

The main clinical objective of LAMPOON is to allow TMVR without causing death from acute severe LVOT obstruction, which often is greater than 100 mm Hg. This is in contrast to MVR or TMVR in patients who are not believed to be at risk of life threatening LVOT obstruction.

¹ Guidance for the Public, Industry, and CMS Staff Coverage with Evidence Development Document Issued on November 20, 2014, https://www.cms.gov/medicare-coverage-database/details/medicare-coverage-document-details.aspx?MCDId=27

There are few data to guide clinical estimations of acceptable thresholds for iatrogenic LVOT obstruction. As for other elements of this protocol, we sought and found guidance in hypertrophic cardiomyopathy, which is a better-characterized but related phenotype of non-valvular LVOT obstruction.

Based on these data we estimate that residual iatrogenic LVOT obstruction less than 50mm is tolerable, because by consensus^{21, 22} it appears not sufficiently severe to warrant surgical intervention in HCM. Moreover, a systematic review by Maron ²³ distinguished obstructive from non-obstructive HCM at a threshold of ≥50 mm Hg. In addition, there is evidence that peak-instantaneous echocardiographic assessment of LVOT gradient appears to correspond to an equivalent catheter peak-to-peak measurement of LVOT gradient, in contrast to valvular aortic stenosis where the echocardiographic measurement corresponds to a lower catheter peak-to-peak LVOT gradient²⁴.

The primary endpoint is designed around the MVARC guidelines¹⁹, to allow comparison with other mitral valve implantation trials, although tailored for the unique features of LAMPOON TMVR. We believe these data and guidelines justify a residual LVOT threshold of up to 50 mm Hg as a component of the study **primary** endpoint.

However, we concur with the FDA reviewer that the gradient in 0 is not optimal, especially in a patient with cardiomyopathy treated for pure mitral valve regurgitation. Therefore, we introduced a co-primary endpoint in 10.2.2 with a lower allowed peak LVOT gradient.

10.2.5 Independent Clinical Events Adjudication

An independent Clinical Events Adjudication Committee will review all of the following that occur in the first year:

- Deaths
- Primary endpoints
- Valve embolization events
- Site-reported strokes

The CEAC will classify relatedness of the above events to the LAMPOON procedure.

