6.0 STUDY DESIGN

6.1 Schematic of Study Design

6.2 Overview of Study Design

This is a prospective, open-label, single-arm, multi-center, investigator-initiated, independently-adjudicated trial of LAMPOON immediately before transcatheter antegrade transseptal TMVR in subjects otherwise ineligible for TMVR.

Candidates will be identified by the participating structural heart disease programs. In evaluation of mitral valve disease, candidates will undergo clinical evaluation including transesophageal imaging and contrast-enhanced gated cardiac CT. Eligibility will be reviewed and proposed by the local multidisciplinary heart teams. Candidates will then undergo central eligibility review by the sponsor and designated investigators. If deemed eligible, candidates will be offered participation in the study.

Once enrolled, subjects will undergo baseline assessment, which includes quality of life questionnaires, walking tests, frailty assessments, and blood tests.

Subjects will be admitted to the hospital and undergo TMVR with LAMPOON. They will undergo endpoint assessment before discharge, after 30 days, 6 months, and then 12 months.

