10.2 Study Analysis

Clinical events are classified by the local site Principal Investigator and confirmed by the Principal Investigator. The results of the study will be released within 12 months of study completion.

Analyses will be stratified according to the setting for TMVR, whether valve-in-ring, valve-in-band, or valve-in-MAC.

The study will be analyzed using descriptive statistics, including a case-by-case narrative summary of major adverse events. Afterwards, we will survey for parameters associated with an increased risk of major adverse events.

Primary and secondary endpoints will also be analyzed separately among patients with- and without- mitral annular calcification as the primary indication for TMVR.

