- LAMPOON device failure including failure to traverse, to lacerate, or to position catheters or guidewires
- Valve malposition, reposition, dislocation, migration, or embolization or deployment in unintended location
- Interatrial shunt

- LVOT gradient
- Aortic valve injury
- Paravalvular leak
- Atrial-ventricular conduction defects to include bundle branch block and complete heart block requiring placement of a temporary or permanent pacemaker
- Cardiac arrhythmia including ventricular tachycardia and atrial fibrillation
- Transient myocardial dysfunction attributed to rapid ventricular pacing required for mitral valve implantation, including brady-asystole or pulseless electrical activity, or requiring cardiopulmonary resuscitation
- Angina and myocardial ischemia
- Coronary artery obstruction or injury that may require intervention
- Myocardial infarction
- Congestive heart failure or BNP elevation
- Cardiogenic shock that may require intervention
- Infective endocarditis
- Left ventricular or left atrial perforation
- Pericardial effusion or tamponade
- Hypertension
- Hypotension requiring vasopressor support or mechanical circulatory support
- Stroke or TIA or seizure
- Hemolysis which requires transfusions and which requires confirmatory dramatic schizocytes and haptoglobin decline
- Low platelets or thrombocytopenia or increased or reduced leukocytes
- Mechanical injury to the myocardium, access vasculature, cardiac valves that may require intervention or that may elevate Troponin
- Bleeding causing anemia and blood transfusions
- Mitral valve thrombosis
- Embolization of air, calcific valve material, atheroma, or thrombus to coronaries, brain, limbs, or viscera causing myocardial infarction, stroke, or limb ischemia
- Retroperitoneal bleed or hematoma or access site injury
- Contrast-induced nephropathy requiring temporary or permanent hemodialysis or medical treatment
- Volume overload, pleural effusion, or dyspnea from procedure-related volume perturbations
- Respiratory failure requiring oxygen or mechanical support or mechanical ventilation
- Infection including access site or urinary or pulmonary or including sepsis
- Pain including back pain and access site and generalized
- Cardiac arrest
- Death

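### Only events the site already calls stroke trigger neurological adjudication, and the committee is asked only about relatedness, so a stroke misclassified in either direction can go uncorrected

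*Combined protocol and SAP*

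**What the plan says.** Section 6.2 presents the design in these terms: "This is a prospective, open-label, single-arm, multi-center, investigator-initiated, independently-adjudicated trial".

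Section 10.2.5 sets the committee's scope: "An independent Clinical Events Adjudication Committee will review all of the following that occur in the first year". Four items follow: deaths, primary endpoints, valve embolizations and "Site-reported strokes". The section then gives one task: "The CEAC will classify relatedness of the above events to the LAMPOON procedure". It does not say that the committee confirms, rejects or re-labels an event.

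On who labels events, section 10.2 says: "Clinical events are classified by the local site Principal Investigator and confirmed by the Principal Investigator".

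Section 10.2.3 lists two relevant exploratory outcomes: "Neurological events as reported by the site clinicians only" and "Pre-discharge stroke, alone, and in combination with the primary endpoint".

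Section 11.1 puts three neurological diagnoses on one line of its list of anticipated device effects: "Stroke or TIA or seizure". Only the first of the three appears in 10.2.5.

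Neither the events table in 6.4 nor the visit schedule in 6.5 includes a protocol neurological examination or stroke scale.

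**The concern.** The boundary between stroke and TIA, seizure or another acute neurological event is a matter of judgement, and it is where independent adjudication is most useful. Here the judgement is made before the committee sees anything, by an investigator who knows the procedure and may have performed it. The wider set of neurological events is already collected under 10.2.3 but is not passed on.

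Stroke is not a remote issue for this technique. Section 12.2 names thromboembolism causing stroke among the anticipated risks of LAMPOON, and Appendix A lists cerebral thromboembolism from guidewire electrification at severity 4. What is at stake is how far the pre-discharge stroke rate, alone and combined with the primary endpoint, can be presented as independently adjudicated. With 30 treated subjects, one label matters.

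**Working it through.** **1. Routes to the committee, as written**

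| Event in the first year | Stated trigger in 10.2.5? | Stated committee decision |
|---|---|---|
| Fatal stroke, any label | Yes, as a death | Relatedness |
| Non-fatal event the site calls stroke | Yes | Relatedness |
| Non-fatal true stroke the site calls TIA, seizure or other | No, unless the subject also has a primary-endpoint or valve-embolization review | None |
| Non-fatal TIA over-called as stroke | Yes | Relatedness; no stated power to re-label |

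Rows three and four are the gap. Primary-endpoint review does little for row three: both co-primary endpoints (10.2.1, 10.2.2) are judged when the subject leaves the catheterization laboratory and have no stroke component, so their review is not designed to find a stroke that appears later in the admission.

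**2. Size of one misclassified subject**

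The plan gives no assumed stroke rate, sample-size calculation or misclassification rate, so there is no figure of its own to reproduce. Section 10.1 gives n = 30 treated subjects. One subject is 1/30 = 3.3 points. Exact (Clopper-Pearson) 95% intervals are:

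- 0/30 = 0% (0 to 11.6)
- 1/30 = 3.3% (0.1 to 17.2)
- 2/30 = 6.7% (0.8 to 22.1)
- 3/30 = 10.0% (2.1 to 26.5)

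These intervals describe sampling error. They show the scale of one event but do not measure misclassification. For the outcome that combines stroke with the primary endpoint, one label moves the result by 3.3 points only if that subject did not already fail on the primary endpoint.

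**3. Direction of any net bias**

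Let p be the true stroke rate, Se the probability that the site labels a true stroke as stroke, and FP the probability that it labels a subject without stroke as having one. All three are assumptions: p = 3%, 7%, 10%; Se = 0.6, 0.8, 1.0; FP = 0 to 3%.

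- *Committee judges relatedness only (as written):* expected observed rate = p·Se + (1 − p)·FP.
- *Committee could also reject false strokes but not add missed ones:* expected observed rate = p·Se.

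As-written examples at p = 7%, Se = 0.8:

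- FP = 0: 0.07 × 0.8 = 5.6%, bias −1.4 points.
- FP = 2%: 0.056 + 0.93 × 0.02 = 7.46%, bias about +0.5 points.

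Extremes over the grid, as written:

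- Lowest (p = 10%, Se = 0.6, FP = 0): 6.0% observed, bias −4.0 points.
- Highest (p = 3%, Se = 1.0, FP = 3%): 3.0% + 0.97 × 3% = 5.91% observed, bias +2.9 points.

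The bias changes sign at FP = p(1 − Se)/(1 − p). At Se = 0.8 this is 0.03 × 0.2/0.97 = 0.6%, 0.07 × 0.2/0.93 = 1.5% and 0.10 × 0.2/0.90 = 2.2% for p = 3%, 7% and 10%.

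Under the second rule the bias is never upward (0 to −4.0 points), but 10.2.5 does not state that rule.

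**The case against.** **Other checks exist.** The study Principal Investigator confirms site classifications (10.2). Serious adverse events are evaluated by the sponsor (11.2.4) and reviewed by institutional IRBs (10.3). Monitors compare case report forms with source documents (11.2.3, 15.3). A mislabelled stroke could be noticed, corrected and then adjudicated. This stands as a mitigation. It is not independent reclassification: confirmation stays within the study team, and no text asks monitors to separate stroke from TIA or to refer an event to the committee.

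**The choice is disclosed and the outcome is exploratory.** Section 10.2.3 says openly that neurological events come from site clinicians alone. Stroke is in neither co-primary endpoint nor the mortality stopping rules (10.3.1, 10.3.2). Analysis is descriptive with case narratives, and there is no comparator, so no between-arm bias. A stroke labelled TIA would still be counted among neurological events. All of this stands and limits the importance of the point.

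**The protocol rates the risk low.** Appendix A gives thromboembolism from guidewire electrification a score of 4, in its lowest band. That bears on how many strokes to expect, not on whether those that occur are labelled correctly.

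**A stronger reading is tempting.** A reader might infer that review can never recover a missed stroke and that the stroke rate can only be too low. The documents do not support either. Deaths, primary endpoints and valve embolizations are also reviewed, so some unlabelled strokes, and every fatal one, do reach the committee. A strictly downward bias also requires a committee that removes false strokes, and the only stated task is relatedness, so a site over-call stays in the count.

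**Conclusion.** The gap is in the text. The only neurological trigger is the site's own stroke label, and the committee has no stated power to reclassify. For non-fatal events with no other trigger, misclassification in either direction can go uncorrected in the pre-discharge stroke outcomes.

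The size is 3.3 points per misclassified subject among 30. The net direction and amount cannot be known from the documents: over the assumed ranges above, the expected bias runs from −4.0 to +2.9 points, and the actual number misclassified may be zero. The conclusion rests on reading 10.2.5 as a complete statement of triggers and tasks; a committee charter giving wider powers would narrow it, but none is cited there.

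Low to moderate importance. It does not affect the co-primary endpoints or the stopping rules. It does affect how far the stroke result can be called independently adjudicated.

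**What to change.** In 10.2.5:

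1. Replace "Site-reported strokes" with all site-reported neurological events: stroke, TIA, seizure or any other new neurological event. Say briefly what the last category covers.
2. Have the committee classify each event as stroke, TIA or other, in addition to its relatedness to LAMPOON.

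In 10.2.3, state that the committee's classification is the one used for pre-discharge stroke, both alone and combined with the primary endpoint. Where it differs from the site's label, report both.

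The cost is a few more dossiers for a committee that already exists, built from events already collected, with no added visit or imaging. The reported stroke rate may turn out higher. The change does not reach events that the site fails to recognise or report at all, since the trigger is still a site report; that limit should be stated with the results.

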2.0 OBJECTIVE

[figure not shown]
The objective of this protocol is further to characterize the feasibility and safety of intentional laceration of the anterior mitral leaflet to prevent left ventricular outflow tract obstruction (LAMPOON), in patients who require transcatheter mitral valve replacement (TMVR) for native mitral valve failure, but who are at risk of left ventricular outflow tract (LVOT) obstruction.

In this protocol, we use a transcatheter heart valve (THV), marketed for implantation in the aortic or pulmonic positions, off-label. The THV device is the Sapien 3 marketed by Edwards Lifesciences.

It is important to discriminate the principal research objective, which is evaluation of the LAMPOON technique, from the off-label use of the significant risk medical device, the Edwards Sapien 3 THV, which is used in the clinical TMVR procedure.

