11.0 ADVERSE EVENT REPORTING

11.1 Definitions

Adverse events: Any untoward medical occurrence in a human subject, including any abnormal sign (e.g., abnormal physical exam or laboratory finding), symptom, or disease, temporally associated with the subject's participation in the research, whether or not considered related to the subject's participation in the research.

This will include:

- Expected events related to the subject's disease process during active enrollment in the research protocol and do not directly result from use of the investigational device or study.
- Procedural events directly related to the cardiac catheterization procedure and recovery from the procedure and do not directly result from use of the investigational device.

Serious Adverse Event (SAE): A serious adverse event that results in any of the following and NOT directly related to the device. This includes any event that

- Results in death
- Is life-threatening (places the subject at immediate risk of death from the event as it occurs);
- results in in-patient hospitalization or prolongation of existing hospitalization;
- results in a persistent or significant incapacity;
- results in a congenital anomaly/birth defect (not relevant to this study); or
- based upon appropriate medical judgment, may jeopardize the subject's health and may require medical or surgical intervention to prevent one of the other outcomes listed in this definition.

Adverse Device Effect (ADE): Any untoward or unintended response to a medical device. This definition includes any event resulting from insufficiencies or inadequacies in the instructions for use or the deployment of the device or any event that is a result of user error.

During this clinical investigation an event should be considered related to the device when it is the result of:

- LAMPOON procedure
- Edwards Sapien 3 transcatheter heart valve or accessories
- Asahi-Intecc Astato XS 20 guidewire

An event will be considered NOT related to the LAMPOON procedure when it is the result of:

- A pre-existing medical condition
- Clearly attributable to TMVR but not LAMPOON part of procedure (example: commissural paravalvular leak)

Anticipated Adverse Device Effects (AADEs): An AADE is an adverse event with a reasonable possibility that the device or procedure caused or contributed to the event. The following AADEs are considered anticipated based on previous human experience:

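### The independent committee reviews every first-year death but is assigned only LAMPOON relatedness, leaving cardiovascular cause, TMVR relatedness and most of periprocedural status to the investigators

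*Combined protocol and SAP*

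**What the plan says.** Four places in the combined protocol and SAP bear on the point.

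- **Section 10.2.3** lists the mortality endpoint as "Mortality, all-cause, cardiovascular vs non-cardiovascular, peri- vs non-periprocedural, LAMPOON and TMVR relatedness". It stands under the heading "10.2.3 Exploratory Endpoints".
- **Section 10.2.5** sets the committee's scope: "An independent Clinical Events Adjudication Committee will review all of the following that occur in the first year". Its list has four items, the first of which is deaths. The only classification named is in its last line: "The CEAC will classify relatedness of the above events to the LAMPOON procedure".
- **Section 10.2** gives the general rule: "Clinical events are classified by the local site Principal Investigator and confirmed by the Principal Investigator".
- **Section 6.2** describes the study as an "investigator-initiated, independently-adjudicated trial of LAMPOON".

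Section 11.1 adds the rule that separates the two parts of the procedure. One ground for calling an event not LAMPOON-related is "Clearly attributable to TMVR but not LAMPOON part of procedure (example: commissural paravalvular leak". The other is a pre-existing condition.

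**The concern.** Section 2.0 says: "It is important to discriminate the principal research objective, which is evaluation of the LAMPOON technique, from the off-label use". For deaths, that separation depends on who judges LAMPOON relatedness, who judges TMVR relatedness, and whether the two judgements are made together. As written, the committee makes the first and the investigators make the second.

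The cardiovascular death count is likewise investigator-classified in a trial described as independently adjudicated. The disclosures at the front of the protocol report proctoring, consulting or research-support ties between some non-NIH investigators and the maker of the Sapien 3 valve. They do not say which investigators classify events. Independent adjudication exists so that a reader need not ask.

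**Working it through.** The plan states no figure to reproduce. The check matches each classification that the endpoint requires to the party the text assigns.

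**Step 1. Who classifies what, for a first-year death.** All-cause death needs no classification. The four others are:

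| Required in 10.2.3 | Assigned to the CEAC in 10.2.5? | Otherwise |
|---|---|---|
| LAMPOON relatedness | Yes | – |
| TMVR relatedness | Not named | Investigators, under 10.2 |
| Cardiovascular or not | Not named | Investigators, under 10.2 |
| Periprocedural or not | Not named; partly reached through the primary endpoints | Remainder to investigators, under 10.2 |

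The qualification in the last row arises because the CEAC also reviews primary endpoints. Absence of procedural mortality is a component of both the primary (10.2.1) and co-primary (10.2.2) endpoints, which are measured at exit from the catheterization laboratory. The documents define no periprocedural window, so they do not show how much further that category extends.

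**Step 2. Does another section fill the gap?**

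- Section 11.2.2 grades relatedness to the research protocol as a whole and does not separate TMVR from LAMPOON.
- Section 11.1 pools the LAMPOON procedure, the valve and the guidewire when it defines a device-related event.
- Section 10.1 commits to consensus guidelines as far as possible, but does not say who classifies deaths.

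None of these gives the CEAC the missing classifications.

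**Step 3. Can the two relatedness calls conflict?** Applying the two grounds in 11.1:

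| CEAC on LAMPOON | Investigators on TMVR | Reading |
|---|---|---|
| Related | Related | Legitimate: both contributed |
| Related | Not related | Legitimate: LAMPOON alone |
| Not related, pre-existing condition | Not related | Legitimate: underlying disease |
| Not related, pre-existing condition | Related | Different view of the cause, but 11.1 sets no rule on TMVR relatedness that this breaks |
| Not related, clearly due to TMVR | Related | Consistent |
| Not related, clearly due to TMVR | Not related | Conflict |

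Only the last row contradicts itself. The plan does not say which call would prevail.

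**Step 4. Size.** The planned number treated is 30 (10.1). The anticipated 30-day mortality is 10% or less for valve-in-ring and valve-in-band (10.3.1) and 30% or less for valve-in-MAC (10.3.2).

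- All 30 in ring or band: 30 × 0.10 = 3 deaths at the anticipated ceiling.
- All 30 in MAC: 30 × 0.30 = 9 deaths at the anticipated ceiling. A mixed enrolment lies between.
- One reclassified death: 1/30 = 3.3 percentage points of treated subjects, or from 1/9 = 11% to 1/3 = 33% of those deaths.

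The documents anticipate no one-year mortality, so deaths between day 30 and one year are additional and unquantified.

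**Step 5. What is not touched.** The stopping rules in 10.3.1 and 10.3.2 count deaths within 30 days whatever the cause. Survival to discharge and to 30 days (Protocol Summary, 1.0) needs no attribution.

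**The case against.** The strongest reply is that 10.2.5 does not say the committee classifies nothing else. It names one required output. A committee charter, which is not among the documents, might cover the rest. This stands as a limit: the finding is about what the protocol text assigns. If a charter covers the other classifications, the protocol should be brought into line with it.

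A second reply is that directing independent review at LAMPOON relatedness is a coherent choice, because LAMPOON is the principal research question and the valve belongs to the clinical procedure. Also, to apply 11.1 the committee must already consider TMVR as an alternative cause. Both are fair. But considering TMVR as an alternative is not a recorded TMVR-relatedness classification, and 10.2.3 reports one.

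A third reply is that little depends on this. The endpoint is one of many exploratory ones, the analysis is descriptive, and 10.2 promises case-by-case narratives of major adverse events, so readers may be able to judge attribution for themselves. This stands and sets the weight of the point.

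A reader might go further and infer any of the following, which the documents do not support:

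- **That a death related to both parts, or to neither, is contradictory.** Step 3 shows that both are legitimate results under 11.1.
- **That periprocedural death rests wholly on the investigators.** Procedural mortality reaches the committee through the primary endpoints.
- **That the investigators' calls would be biased.** No misclassification rate or direction is given, and 1/30 holds for any binary event in 30 subjects. Knowledge of treatment does not distinguish the parties either: in an open-label, single-arm trial the committee knows it too.

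**Conclusion.** The point holds as a gap in assignment. Of four classifications that the mortality endpoint requires, one is expressly given to the independent committee. Cardiovascular cause and TMVR relatedness are left to the investigators, as is periprocedural status beyond the procedural-mortality component. For these, the description in 6.2 is not carried through.

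The consequence is modest: an exploratory breakdown of few deaths, with one narrow combination of calls that would conflict and no rule to settle it. A reader might infer that the trial's mortality result or its safety monitoring is compromised. It is not, since both rest on all-cause death.

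The conclusion assumes that the general rule in 10.2 governs whatever 10.2.5 does not assign, and that no charter outside these documents says otherwise. The change is a cheap improvement, not the repair of an error in the primary analysis.

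**What to change.** Amend the last line of 10.2.5 so that, for each first-year death, the CEAC classifies the following in one review:

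1. cardiovascular or non-cardiovascular cause;
2. periprocedural or not, with the definition written into the protocol, for example that of the MVARC guideline the plan already follows;
3. LAMPOON relatedness;
4. TMVR relatedness.

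Having one body make both relatedness calls together removes the split in responsibility that allows the conflict in Step 3.

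In 10.2.3, state that the CEAC classification is used for first-year deaths. Vital status is collected to year 5 (6.4, 6.5) but the committee's remit ends at one year, so also state that deaths after year 1 are investigator-classified and reported separately. Otherwise the endpoint would mix two sources without saying so.

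If the sponsor prefers not to widen the committee's task, the minimum is a sentence in 10.2.3 saying which mortality categories are investigator-assigned.

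The cost is three more fields on the committee's form and slightly longer review of files it already receives. No new data collection from subjects is needed.
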